# **Human Subjects Protection Information**

### 4. . Participants:

**a. Number:** 500 **Age range:** 18-70 **Gender:** Any, though the population is likely to be mostly female as hEDS/HSD affects more women than men.

## b. Recruitment population, including inclusion/exclusion criteria:

Because the Pilates program is on-line, subjects may participate from anywhere in the world.

- a. Inclusion criteria:
  - i. Have some form of HSD/hEDS diagnosed by any health care provider; this would include individuals diagnosed with Joint Hypermobility Syndrome using the pre-2017 diagnostic criteria.
  - ii. Able to read the English language and understand spoken English.
  - iii. Willing to try to do Pilates using the 25 minute on-line training videos at least 3 times per week, unless they experience some adverse event or illness that prevents them from safely participating.
- b. Exclusion criteria
  - Medical restrictions (such as recent and healing surgery, fractures, comorbidities such as severe rheumatoid arthritis or neurological conditions, etc.) that prevent them from safely doing gentle exercise lying down on the floor, sitting, and standing.
  - ii. Inability to safely stand (with or without using upper extremity for balance) for

- 10 consecutive minutes.
- iii. Recent injuries or changes in status that are not stable. This will be defined as "A significant change in your wellness due to recent injury or new symptoms in the past month that result in your wellness during the past month being very different from the past 5 months. Flare episodes that are typical for you will not prevent you from participating at this time."
- iv. Significantly changed treatment approach or medication within the past 3 months or be expecting to change their treatment program (including medication changes) during the study. This would make it difficult for us to know if changes are due to the Pilates class or the change in their treatment program. However, we understand that their health status may change such that they need to change their health care routine for physical and mental health.
- v. Currently receiving regular rehabilitation such as physical therapy, or having received PT or a similar movement-based therapy (such as such as Pilates, Feldenkrais, Tai Chi, qigung, yoga) in the past 3 months. Individuals who continue to do exercises from any of these sources are not excluded, as these individuals should be stable on their current routine.
- vi. Currently doing more than 30 minutes/week of Pilates exercise.
- vii. Under 18 years old or over 70 years old.
- **c. Recruitment procedures** (Attach advertisements or recruitment notices as labeled appendices. Do not begin recruiting until you have an approved protocol.):

Recruitment posters, emails and social media postings will include the information shown in Appendix A. For locations that require a shorter announcement, the brief recruitment notice (Appendix A2) will be used, and will link to the full recruitment notice.

- a. The EDS Society website allows requests to be submitted online and distributed to their subscribers link: https://www.ehlers-danlos.com/research-survey-submission/
- b. Social Media via [name] Facebook, Twitter and Instagram accounts
- c. Social media and support groups specifically for those with EDS / HSD
- d. Website announcement on www.[name]
- e. Notice in the instructor's Pilates studio
- f. Snowball sampling through current clients and database of [name], who will be given or emailed the recruitment notice. Many of the current or past clients would themselves be excluded, as they already participate regularly in Pilates. But, they may know other people who could participate.

## d. Incentives and compensation

Subjects will be able to use the on-line Pilates course "Strengthen Your Hypermobile Core" during the study (8 weeks of intervention and 6 months of follow-up) for free . Subjects who complete the study (8 week and 6 month questionnaires) will be given permanent access to this course as incentive to complete the study.

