# e. Group assignment method

This is a pre-test/post-test design and all subjects will serve as their own control, as we will be measuring change over time. The wait-list group will also serve as a comparison group. Because of high demand, groups will be assigned in a pragmatic way, with those already enrolled in the immediate start group, and the next, equal number in the 8-week control group. Assignment is therefore determined by when they consent and complete the initial survey.

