sessions and, if so, why. We will also ask if they have any comments about the modules or about their experience. We will also ask about any changes in pain, either related to the Pilates practice, or unrelated. The contact email will also remind them that they can contact one of the PI (JD) if they have questions or problems with the Pilates, or (LR) if they have any questions about research participation.

At the end of 8 weeks, subjects will be asked to repeat the initial questionnaires on SurveyMonkey, and comment on their experience doing the Pilates. This is likely to take about 60 minutes. Subjects will continue to have access to the Pilates modules and we will encourage them to continue using the modules. We will track whether individuals do access the modules over the next 6 months.

Six months after subjects complete the 8 week exercise session, we will contact each subject again and ask him/her to repeat the initial questionnaires on SurveyMonkey, and again comment on whether they felt the Pilates was helpful.

We will also include an 8-week wait-list group constructed from subjects asking to participate after we have already recruited 225 subjects. This wait list is primarily because we do not want to be so overwhelmed by participants that we cannot manage them effectively (responding to questions about the Pilates, sending out follow-up surveys, etc.). Also, a wait-list group would provide a control group (albeit not randomly selected). All participants who do not start in the initial group will be asked if they still want to participate in a wait-list group; if they do, we will contact them 8 weeks after their initial surveys were completed, ask them to repeat the surveys, then start them in the Pilates program.

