### e. Analysis of outcomes:

- Quantitative data will be coded and entered into Excel, reviewed for outliers, and transferred to SPSS
- Descriptive statistics related to demographics and initial scores for BIoH, IPAQ, TSK-11, R-BARQ
- Descriptive statistics related to subjects use of the different modules (which Pilates modules were used during each of the 8 weeks and overall), and continued use of the modules through the 6 month follow-up.

- Repeated Measures ANOVA comparing pretest, post-test (8 wk) and 6 month after post-test: BIOH, IPAQ, TSK-11, R-BARQ
- ANOVA comparing change over 8 weeks for the Pilates group vs. the wait-list group: BloH, IPAQ, TSK-11, R-BARQ
- Regression analysis using IPAQ, TSK-11, R-BARQ to predict quality of life and function as measured using BloH before intervention, after intervention (including compliance) and 6 months later (including compliance).
- Qualitative analysis of the narrative (email) information using content analysis using the following process:(Bengtsson, 2016)
  - o Decontextualization to identify meaning units, create code list
  - o Recontextualization to verify that all important information has been coded
  - o Categorization to organize themes, with triangulation by investigators
  - Compilation to formulate conclusions, audit, member check if subjects agree

We understand that the lack of a randomized control group makes our current design less rigorous than a randomized control trial (RCT), but having a wait-list comparison group makes the design stronger.

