# Thank you for participating in this research

### Appendix I.1: Email requesting Follow-Up Health History after 8 weeks of Pilates and at 6 month follow-up.

Thank you for participating in "Assessing the Impact of Internet-Guided Pilates Training on People with Hypermobility."

We hope you are continuing to do the Pilates exercises, but remember that you should only do what you feel is appropriate for you. All subjects have access to the Pilates videos during the 8 initial weeks of the study and 6 months of follow up, whether or not you do the Pilates exercises. Subjects who complete the 8 week and 6 month follow-up surveys will also be given permanent access to the on line Pilates modules.

You may contact [name] if you have questions about the Pilates program, but please do not share information regarding your response to the research questions in SurveyMonkey, as [name] is "blinded" to the research data (for scientific validity and to protect your private information, she is not supposed to know how individual subjects respond to the research questions). Please do not Reply to this email. If you would like to contact [name] with questions about the Pilates program, please email her directly at: [contact].

Append	lix I.2: Foll	ow-Up Health History after 8 weeks of Pilates and at 6 month follow-up.  The 3 first letters of the month (in English) of your MOTHER'S birthday (e.g., SEP)					
		YOUR 2-digit birthday date (e.g., Ø8 for May, 8th) The first letter of YOUR MIDDLE NAME; enter X if you do not know or have a middle name (e.g. M for Mary) The total number of OLDER SIBLINGS you have, including living, deceased, and half (e.g., 0 if you are an only child enter 9 if you have 10 or more siblings)					
	• In this	s example, the identification code would be SEP08M0 (SEPØ8MØ)					
Your 7-ch	naracter ID C						
-	=	ons will either state "8 weeks" or "6 months" depending on which time the survey is done] Did your health care program change significantly during the course of this research?					
2.		Did you have any increased pain or problems in the past 8 weeks (6 months), beyond eness from doing new exercises, that you think was due to the Pilates exercises?					
	a.	If so, briefly describe.(narrative)					
3.		Did you have any injuries or increase in symptoms during the past 8 weeks (6 months) ed to the Pilates program, that has affected your ability to do the Pilates exercises					

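### The 8-week survey carries different incentives in the two groups, so selective response may tilt the only between-group test towards Pilates

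*Combined protocol and SAP*

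**What the plan says.** **Groups.** Assignment follows order of enrolment. The wait-list is "constructed from subjects asking to participate after we have already recruited 225 subjects", and Section 4e makes it "the next, equal number in the 8-week control group".

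**Wait-list survey.** Under Section 6a, the team contacts wait-list subjects 8 weeks after their initial surveys and will "ask them to repeat the surveys, then start them in the Pilates program". Their comparison survey is thus the step before the course begins.

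**Immediate starters' survey.** Appendix I.1 tells them: "All subjects have access to the Pilates videos during the 8 initial weeks of the study and 6 months of follow up". The same sentence says that this does not depend on exercising, and nothing ties it to returning the 8-week survey. The only completion reward is in Section 4d: those who return both the 8-week and the 6-month questionnaires "will be given permanent access to this course as incentive to complete the study".

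**Test.** Section 6e plans an "ANOVA comparing change over 8 weeks for the Pilates group vs. the wait-list group", covering BIoH, IPAQ, TSK-11 and R-BARQ. It states no missing-data method, analysis set or comparison of responders with non-responders.

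**The concern.** A change score needs both surveys, so without a missing-data method the between-group ANOVA describes only people who answered at week 8. For a wait-list subject who still wants the course, the survey comes just before the thing they are waiting for. For an immediate starter, it brings nothing at that moment. It counts towards permanent access to a course that a person who stopped in pain or saw no benefit has little reason to want.

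Liking the course could plausibly track the outcome. Appendix I.2 lists hurting too much and discomfort among the reasons for not doing Pilates, and the primary outcome, the BIoH, scores pain, fatigue and function. If poor responders in the Pilates group answer less often, the group difference is pushed in favour of Pilates. This selection arises after entry, from experience during the 8 weeks, so baseline adjustment alone would not fully remove it. It is also separate from the non-random allocation that the plan acknowledges in Sections 3 and 6e.

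Section 2 says that encouraging findings would make a randomised trial the natural next step, so an inflated difference could mislead the planning of that trial.

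**Working it through.** **The plan's own figures.** Section 4a gives 500 participants with no alpha, power, effect size, SD or dropout, so 500 cannot be reproduced from a formula. Section 6a gives 225 immediate starters, and an equal wait-list makes 2 × 225 = 450. That difference does not bear on this point. No retention figure is given, so what follows is illustrative.

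**Assumed inputs.** 225 per group (from Sections 6a and 4e); half the Pilates group like the course (q = 0.5); true group difference zero; SD of change 1; wait-list response 80% and unrelated to change (180 responders); two-sided alpha 0.05. Let g be the gap in mean change between likers and non-likers, in SD units, and rL and rN their response rates.

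**Formulas.**
- Share of likers among Pilates responders: s = q·rL / (q·rL + (1 − q)·rN)
- Bias towards Pilates: b = g·(s − q)
- Standard error: se = √(1/nP + 1/180), with nP the number of Pilates responders
- Type I error: Φ(b/se − 1.96) + Φ(−b/se − 1.96)

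**Worked case.** With rL = 80%, rN = 40% and g = 0.8: s = 0.40/0.60 = 0.667; b = 0.8 × 0.167 = 0.133; nP = 225 × 0.60 = 135; se = √(1/135 + 1/180) = 0.114; type I error = 0.216.

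| Response, likers / non-likers | s | Bias in SD at g = 0.25, 0.5, 0.8 | Type I error at g = 0.25, 0.5, 0.8 |
|---|---|---|---|
| 70% / 70% | 0.500 | 0, 0, 0 | 0.05, 0.05, 0.05 |
| 80% / 70% | 0.533 | 0.008, 0.017, 0.027 | 0.051, 0.053, 0.057 |
| 80% / 60% | 0.571 | 0.018, 0.036, 0.057 | 0.053, 0.062, 0.082 |
| 90% / 50% | 0.643 | 0.036, 0.071, 0.114 | 0.062, 0.10, 0.18 |
| 80% / 40% | 0.667 | 0.042, 0.083, 0.133 | 0.065, 0.113, 0.216 |

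If g = 0, the bias is zero at any response rates.

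**Scale.** The difference detectable with 80% power is (1.96 + 0.84) × √(2/225) = 0.26 SD with everyone answering, and 0.30 SD at 180 per group.

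**When there is a true effect.** Suppose that non-likers and the wait-list do not change. The true mean effect is then 0.5g and the observed one is s·g, so the inflation is s/0.5: 1.14 at 80%/60%, 1.29 at 90%/50% and 1.33 at 80%/40%. In the upper scenario, every non-responder had zero change. If responders' mean change is d and a fraction r respond, the truth is r·d + (1 − r)·0, so the inflation is 1/r: 1.25 at 80% response, 1.43 at 70%, 1.67 at 60% and 2.0 at 50%.

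**The case against.** Four stronger readings are tempting, and the documents do not support them.

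- **A reader might infer that the Pilates group will over-represent people who liked the course.** There are no retention data, and the bias vanishes if answering is unrelated to liking or liking is unrelated to change. Only *may* is supportable.
- **A reader might infer that outcome-related non-response is confined to the Pilates group.** Wait-list subjects who flare, improve or lose interest may also fail to answer, and that could act in either direction.
- **A reader might infer that the wait-list is refused the course without the survey.** Section 6a gives a sequence and does not state a condition. Permanent access is also worded for all subjects, so the asymmetry lies in what each group gains at its own 8-week survey. An immediate starter who skips it does forfeit the later reward.
- **A reader might take the 1/r factor as the expected inflation.** It requires that no non-responder changed at all. At the response rates above, the milder model gives 1.14 to 1.33, against 1.43 to 1.67 from 1/r at the same overall response (70%, 70% and 60%).

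The plan also has partial safeguards. Appendix H tells subjects each week that they stay in the study if they answer, however little Pilates they do. Appendix I.1 follows its hope that they are continuing with advice to do only what suits them. Appendix I.2 has a question aimed at people who stopped. Section 7c accepts no Pilates at all.

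All of this stands, and it limits the point. The safeguards permit non-exercisers to answer, but they do not say that those answers are equally needed and do not offset the weaker incentive. Nothing in Section 6e would reveal selective response if it occurred.

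**Conclusion.** The difference in incentive is in the text, and the only between-group comparison has no protection against it. Selective response in the Pilates group is therefore a plausible source of bias in favour of Pilates, but not a demonstrated one.

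Its size is unknown. Under the assumptions above, it is small with mild differential response. With strong differential response and a large gap in change, it reaches about half of the 0.26 SD detectable at 225 per group. These figures rest on an assumed even split of likers and non-likers, unit SD and wait-list response unrelated to change. The recruitment and consent appendices were not available, so any incentive wording there could not be checked.

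This is an inexpensive improvement worth making in a pilot. It does not invalidate the design.

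**What to change.** 1. **Invitation and reminder.** In Appendix I.1, say that answers from people who stopped or did little Pilates are needed just as much as the others. Send one further reminder to all subjects in both groups. A blanket reminder means that the person who holds the email addresses, and is blinded to survey data, need not learn who answered.
2. **Reporting.** Give 8-week response by group. Within the Pilates group, compare responders with non-responders on baseline scores, module use in weeks 1 to 8 and weekly-survey answers. Module use is already logged against the research code (Section 6a). Make these links before emails and codes are discarded (Sections 7b, 7f and 7g).
3. **Sensitivity analysis.** Beside the Section 6e ANOVA, analyse all enrolled subjects, with missing Pilates-group 8-week changes multiply imputed from the wait-list distribution. Do not fill in the wait-list mean as a single value, because that understates the standard error. Some who stopped may have worsened, so the wait-list distribution is not a worst case. Add a version in which non-responders did worse than the wait-list by a margin fixed in advance. State the conclusion in light of all of these.

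The cost is a few lines of email text, one extra mailing and modest additional analysis of data already being collected. The stated benefit may come out smaller.

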# e. Group assignment method

This is a pre-test/post-test design and all subjects will serve as their own control, as we will be measuring change over time. The wait-list group will also serve as a comparison group. Because of high demand, groups will be assigned in a pragmatic way, with those already enrolled in the immediate start group, and the next, equal number in the 8-week control group. Assignment is therefore determined by when they consent and complete the initial survey.

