# 9. Conflict of interest statement:

performed for this device?

One of the researchers (JD) has a financial interest in the Pilates training program being offered. While her role is essential for the intervention and data collection, data analysis will be performed by the other researchers who have no financial interest.

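### Order of enrolment alone decides who starts Pilates and who waits, so the only controlled comparison mixes any Pilates effect with enrolment order, one-sided selection and calendar time

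*Combined protocol and SAP*

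**What the plan says.** Section 4e of the protocol assigns groups in sequence, "with those already enrolled in the immediate start group, and the next, equal number in the 8-week control group", and adds: "Assignment is therefore determined by when they consent and complete the initial survey". Section 6a gives the cut-off: the wait-list is "constructed from subjects asking to participate after we have already recruited 225 subjects". People who miss the first group are asked whether they still want to join as wait-list subjects; the first group gets no such second question. For those who stay, "we will contact them 8 weeks after their initial surveys were completed", and they then repeat the surveys and begin the course.

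The main reason given for the wait-list is workload: "we do not want to be so overwhelmed by participants that we cannot manage them effectively". Having a comparison group is named as a further advantage.

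Objective 1 (section 3) is to compare the course with the wait-list group. Section 6e plans an ANOVA of 8-week change in the BIoH, IPAQ, TSK-11 and R-BARQ between the two groups, and names no adjustment for baseline or calendar time. The protocol acknowledges in sections 3, 6a and 6e that the comparison is not randomised.

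**The concern.** The other planned outcome analyses are within-person or correlational, so objective 1 rests on this one comparison. Three things differ between its two sides besides Pilates.

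- **Order of enrolment.** People who join early may differ from late joiners in motivation, in how they heard of the study, or in their expected course over 8 weeks.
- **One-sided selection.** Only the later enrolees pass a second willingness question, so people unwilling to wait leave that group alone.
- **Calendar time.** Each person's 8 weeks run from about their own enrolment, so the Pilates periods tend to fall earlier than the waiting periods.

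All four outcomes are self-reported questionnaires in an open study. A modest difference in change from any of these sources would be credited to the course, or could hide a benefit. Section 13 of the plan's reasoning is simple: encouraging findings would lead to a formal randomised trial, so a spurious result has a practical consequence.

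**Working it through.** **Inputs from the protocol.** Cut-off 225 (section 6a); wait-list of equal size (4e); total 500 (4a); wait of 8 weeks from each person's own survey (6a). It states no alpha, power, SD, effect size, dropout or recruitment duration.

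**Assumptions.** Two-sided 5% test, normal approximation, no dropout, differences in units of the SD of 8-week change.

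**1. The plan's own figure.** 225 + 225 = 450, against 500 stated. There is no sample-size calculation to reproduce, and 500 is not called wrong here. The steps below use 225 per group, and 275 or 225 for the later enrolees.

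**2. Precision as planned.** SE = √(1/225 + 1/225) = 0.0943 SD. Detectable difference at 80% power = (1.960 + 0.842) × 0.0943 = 0.264 SD.

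**3. False positives with no Pilates effect.** If early and late enrolees differ by b in mean 8-week change for other reasons, the rejection probability is P(Z > 1.96 − b/SE) + P(Z < −1.96 − b/SE).

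| Assumed b (SD) | b/SE | Test significant |
|---|---|---|
| 0 | 0 | 5.0% |
| 0.05 | 0.53 | 8.3% |
| 0.10 | 1.06 | 18.6% |
| 0.15 | 1.59 | 35.6% |
| 0.20 | 2.12 | 56.4% |

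The documents give no value for b, so this is a range and not an estimate.

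**4. Calendar shift.** If people enrol evenly over T weeks, the first half enrols on average T/2 weeks before the second half: 0.5 week for T = 1, 4 for T = 8, 8 for T = 16, 26 for T = 52. Under a random list the average shift is about 0. Since T is not stated, the shift could be trivial or large.

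**5. Does the capacity reason need this rule?** The peak number of people in the 8-week course at one time was simulated for 450 people, under the sequential rule and under a 1:1 list in blocks of 4 with the same wait. Accrual patterns were assumed.

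| Accrual | Sequential | Random list (mean peak) |
|---|---|---|
| Even, 1 to 16 weeks | 225 | 226-227 |
| Even, 24 weeks | 150 | 152 |
| Even, 52 weeks | 70 | 72 |
| Front-loaded, 32 weeks | 225 | 160 |

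Across all patterns tried, including back-loaded accrual, the random list's peak was at most 3 people higher, and sometimes well below. This applies only if everyone is randomised from the start.

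**6. If the first 225 are already committed.** Only later enrolees can be randomised.

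- 500 − 225 = 275, split 137/138: SE = √(1/137 + 1/138) = 0.1206; detectable difference 2.802 × 0.1206 = 0.34 SD.
- 225, split 112/113: SE = √(1/112 + 1/113) = 0.1333; detectable difference 2.802 × 0.1333 = 0.37 SD.
- If the new immediate starters fully overlap the first cohort, the peak is 225 + 112 = 337 or 225 + 137 = 362.

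**The case against.** The strongest defence is that the authors made an open, pragmatic choice. The study is described as a pilot, its base design is pre/post with each subject as their own control, the non-random comparison is admitted repeatedly, and a randomised trial is named as the next step. That stands as a fair description of the aims. Disclosure does not remove the bias from the test of objective 1, and no reason is given for making the later arrivals the ones who wait.

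The wording of section 4e suggests that the first group had enrolled before the wait-list rule applied. If so, those people cannot be randomised now, and the remedy costs precision and possibly workload. This stands. The claim that a random list never needs extra capacity is not supported.

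A reader might infer that the instructor steers recruits into the first group: section 4c lists "Snowball sampling through current clients and database of [name], who will be given or emailed the recruitment notice", and section 9 says "One of the researchers (JD) has a financial interest in the Pilates training program being offered". The documents do not support that reading. Names are removed, nothing says who times the recruitment channels, sign-up is self-service online, other channels include a patient society and support groups, and section 4c expects many current clients to be excluded. Analysis is assigned to researchers without a financial interest.

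A reader might also say that the two groups wait in different seasons. Only one group waits, and rapid enrolment would make the shift small. Nor can it be said that recruitment channel goes unrecorded, since the text of Appendix C is incomplete.

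Finally, random allocation would not blind anyone. People doing Pilates may still expect benefit while those waiting do not.

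**Conclusion.** The point holds in this limited form. Allocation follows enrolment order, with a second willingness question for later enrolees only, so the planned comparison cannot separate a Pilates effect from order, one-sided selection and calendar time. An order-related difference of 0.10 to 0.20 SD would be enough to raise the false-positive rate from 5% to between 19% and 56%. That size is assumed, the direction of any bias is unknown, and the figures rest on 225 per group without dropout. Random allocation would remove the confounding with order and calendar time; expectation effects in self-report would remain. The pre/post, module-use and qualitative aims do not depend on this allocation rule. The change is worth making for everyone who can still be randomised, but the finding does not invalidate the study as a pilot.

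**What to change.** Amend sections 4e and 6a as follows.

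- At consent, ask every subject to accept either start date, which replaces the separate question put to later enrolees only.
- After the initial survey is complete, allot start now or start in 8 weeks from a pre-generated 1:1 list with randomly varied block sizes, keyed to the self-made research code and held by a researcher without a financial interest.
- Name this randomised set in section 6e as the controlled comparison for objective 1.

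**If no start dates have been promised,** randomise everyone. With 225 per group the detectable difference stays at 0.26 SD and the peak load is about the same.

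**If the first 225 are already committed,** randomise only later enrolees. Keep the first cohort for the pre/post, module-use and qualitative aims, and report the comparison by order of enrolment as secondary, with its limitation stated. The price is a detectable difference of about 0.34 SD (275 randomised) or 0.37 SD (225 randomised), and a higher load if the new immediate starters overlap the first cohort.

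In both cases, state the recruitment dates for each group and keep the caution about unblinded self-report. The cost is an IRB amendment, consent wording that the start may be delayed by 8 weeks, and the list itself; no extra staff, surveys or subjects are needed for the allocation.
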